### Drug Development Rationale

Antimuscarinic drugs are the cornerstone of pharmacotherapy in the pediatric NDO population, and have been shown to improve intravesicular pressure, and decrease symptoms. Four antimuscarinic drugs (oxybutynin, trospium chloride, tolterodine and darifenacin) have documented results in the pediatric NDO population (Kennelly & DeVoe, 2008). Of these,

only oxybutynin is widely approved for use in children, and is available as a once a day extended release (XL) tablet, as well as an immediate release tablet. Although effective, oxybutynin use has been limited by a side effect profile which may have particular relevance in the pediatric population where development (eg, physical, cognitive, psychosocial) is still ongoing.

A particular medication's effectiveness is highly dependent on patient compliance which is itself dependent on tolerability. Given individual differences in toleration and the limited choice available there is an unmet need for alternative treatments.

Children with NDO therefore represent a disease population with a need for an alternative effective, safe and well-tolerated therapy to help manage the overactive detrusor, reducing or preventing incontinence, as well as the high pressure bladder contractions that can result in UUT deterioration and renal damage.

Other treatments such as alpha blockers, anxiolytics, tricyclic antidepressants, intravesical oxybutynin, botulinum-A toxin, electrical stimulation and biofeedback, may also be used (Coward & Saleem, 2001) although safety and efficacy have not been reliably demonstrated.

Acetylcholine which interacts with muscarinic receptors at the detrusor is the predominant peripheral neurotransmitter responsible for bladder contraction. Both fesoterodine and oxybutynin are muscarinic receptor antagonists and consequently have a role in mediating detrusor overactivity.

Fesoterodine is an antimuscarinic drug available as a prolonged release (PR) tablet formulation, and is approved in Europe and the USA at doses of 4 mg and 8 mg once daily for the treatment of overactive bladder (OAB) in adults; it is not approved for use in the pediatric population.

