#### **2.1.2. Secondary Objectives**

The secondary objectives of this study are to:

- evaluate the safety and efficacy of fesoterodine versus oxybutynin in pediatric NDO subjects with weight  $>25$  kg.

- evaluate the safety of fesoterodine 4 mg and 8 mg once daily treatment for up to 24 weeks in pediatric NDO subjects with weight >25 kg.
- evaluate the safety of fesoterodine 2 mg and 4 mg once daily treatment for up to 24 weeks in pediatric NDO subjects with weight ≤25 kg.
- determine the steady-state population pharmacokinetics of 5-HMT following fesoterodine 4 mg and 8 mg once daily treatment in pediatric NDO subjects with weight >25 kg.
- determine the steady-state population pharmacokinetics of 5-HMT following treatment with two doses of fesoterodine 2 mg and 4 mg once daily in pediatric NDO subjects.

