#### **2.2.2.2. Safety Endpoints**

- Adverse events, including monitoring of targeted events including, but not limited to:
  - Anticholinergic effects such as dry mouth, dry eyes and constipation.
  - CNS effects such as behavioral changes (eg, aggression), decreased cognitive function, headache, seizures, somnolence.

- Visual effects such as accommodation disorder, blurred vision, and amblyopia.
- Visual acuity and accommodation tests.
- Cognitive function by the Child Behavior Check List and Grooved Pegboard Test.
- Vital Signs, including heart rate in the context of age-appropriate norms.
- Urinary Tract Infection, as evidenced by urinalysis, urine microscopy, culture and sensitivity.
- Clinical Laboratory Evaluations in the context of age-appropriate norms, with particular reference to liver function tests and renal chemistry.
- Post-void residual volume (PVR) in subjects not performing CIC, or with >1 urinary tract infection (UTI) during the study.

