### **9.3. Safety Analysis**

The Safety Analysis Set will be defined separately for each cohort and consists of all randomized subjects who have received at least one dose of study medication in the relevant phase of the study.

For each cohort, results from the safety assessments and any adverse events will be presented in tabular and/or graphical format adhering to current [Pfizer Data Standards](#). These presentations will be split by treatment group, and produced separately for the active comparator/efficacy phase and the safety extension phase. Safety endpoints such as vital signs, laboratory evaluations, weight, PVR, vision testing and CBCL/GPT results will be presented descriptively by treatment group. Adverse event incidence rates will be compared descriptively between treatment arms. An evaluation of withdrawal rates and time to withdrawal will be performed.

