### **8.1.1. Analysis of Continuous Data**

Where data is to be summarized using descriptive statistics the following will be presented: n, mean, standard deviation, median, minimum, and maximum.

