### Tier 2 Adverse Event Reporting

Tier 2 summaries will only report those adverse events which occurred to 4 or more subjects in any treatment group.

The percentage of subjects experiencing a particular adverse event in each treatment group will be presented both in a table and graphically. The table will present the point estimate for the percentage of affected subjects, along with the risk differences and their 95% confidence intervals, for Cohort 1. However for Cohort 2, only point estimates will be presented, as there is no active comparator for this cohort.

Graphical presentations will include the point estimate for the percentage of affected subjects, along with the risk differences and their 95% confidence intervals for Cohort 1, and point estimates only for Cohort 2.

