### Vital Sign Reporting

For vital signs change from baseline will be summarized together with the number of subjects whose blood pressure and heart rate fall outside specified ranges. Furthermore, the number of subjects who decreases and increases in responses fall outside specified ranges will be summarized (for blood pressure only).

| Endpoint                   | Cutoff      |
|----------------------------|-------------|
| Systolic Blood Pressure    | <90         |
| SBP Increase from Baseline | ≥30         |
| SBP Decrease from Baseline | ≥30         |
| Diastolic Blood Pressure   | <50         |
| DBP Increase from Baseline | ≥20         |
| DBP Decrease from Baseline | ≥20         |
| Pulse                      | <40 or >120 |

At all visits, for replicates, the second PVR value should be reported. This should also be the smallest if done per protocol. This should be footnoted as follows: “Only the second PVR urine volume is reported in the summary tables in cases where a repeat PVR assessment is made”.

Visual Acuity (LogMAR units) and Accommodation (the distance for each eye at which vision becomes blurred – the mean of triplicate measurements), CBCL (Domain T Scores and Total Scores as captured in the CRF), GPT (Time to completion, Number of pegs dropped and Number of pegs correctly placed – by dominant/non-dominant hand and whether the 10-peg or 25-peg test was used, separately), Physical Exam and Weight will be summarized by visit and changes from baseline at each visit using descriptive statistics.

For Visual Acuity, LogMAR units will be derived from the Snellen ratios recorded on the CRF, as shown in the table below. The decimal is the Snellen ratio (whether it is recorded in metres or feet) expressed as a decimal and  $\text{LogMAR} = \text{Log}_{10}(1/\text{decimal})$  (recorded to 1 d.p.). Due to the limited space available in the CRF, the Snellen ratio ‘20/12.5’ will be recorded as ‘20/13’, however this should still be converted to a decimal value of 1.60 and a LogMAR value of -0.2 as shown in the table below. If the Snellen Visual Acuity has been recorded in any other format than those shown below, the appropriate conversion to decimal will be determined prior to database lock.

Table 3  
Equivalent visual acuity measurements

| Snellen visual acuity |        |        |         |                  |        |
|-----------------------|--------|--------|---------|------------------|--------|

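### For Grooved Pegboard, CBCL, visual acuity, accommodation and pulse in Cohort 1, no fesoterodine-oxybutynin difference or confidence interval is planned, and the tables do not keep the oxybutynin arm whole

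*SAP*

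**What the plan says.** Protocol 2.1.2 sets a secondary objective, for subjects above 25 kg, to "evaluate the safety and efficacy of fesoterodine versus oxybutynin in pediatric NDO subjects". The Drug Development Rationale in Protocol 1.2 explains the interest: "oxybutynin use has been limited by a side effect profile which may have particular relevance in the pediatric population". Protocol 2.2.2.2 names the vision tests, heart rate and "Cognitive function by the Child Behavior Check List and Grooved Pegboard Test" among the safety endpoints.

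The planned analysis of these measures is descriptive in both documents. Protocol 9.3 states: "Safety endpoints such as vital signs, laboratory evaluations, weight, PVR, vision testing and CBCL/GPT results will be presented descriptively by treatment group". In SAP 8.2.5, under Vital Sign Reporting, one sentence covers LogMAR acuity, accommodation, CBCL and Grooved Pegboard and ends: "Physical Exam and Weight will be summarized by visit and changes from baseline at each visit using descriptive statistics". Pulse comes under another sentence there: "For vital signs change from baseline will be summarized together with the number of subjects whose blood pressure and heart rate fall outside specified ranges". SAP 8.1.1 says that, for descriptive statistics, "the following will be presented: n, mean, standard deviation, median, minimum, and maximum". That list contains no between-arm difference and no interval.

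Other Cohort 1 outcomes are treated differently. SAP 8.2.1 gives maximum cystometric capacity adjusted mean differences from oxybutynin with 95% CIs. Tier 1 adverse events get risk differences with CIs and p-values. Tier 2 events are tabulated "along with the risk differences and their 95% confidence intervals, for Cohort 1".

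SAP 5.3 and 8.2.5 also fix the columns for safety tables other than adverse events and duration of treatment. Oxybutynin subjects appear as three groups: those who moved to fesoterodine 4 mg, those who moved to 8 mg, and those who took oxybutynin only. Protocol 5.2 and 5.3 leave the choice between 4 mg and 8 mg to the investigator.

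**The concern.** Cohort 1 is randomised 1:1:1, and these measures bear on the development and side-effect questions that motivate the comparison. Change from baseline within one arm combines any drug effect with whatever else alters the score over 12 weeks. For a timed dexterity test given at Day 1, Week 12 and Week 24, practice and maturation are plausible contributors. Influences common to all arms cancel only in the difference between randomised arms, and that difference is not planned.

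The column layout makes this worse. A column defined by a dose chosen at Visit 5 or earlier is defined by a decision taken after randomisation, possibly in light of how the child responded. Comparing it with a fesoterodine column is not a randomised comparison. At stake is whether a reader of the report can say, with stated uncertainty, how each fesoterodine dose compares with oxybutynin on the measured safety tests.

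**Working it through.** **1. What is planned, measure by measure (Cohort 1)**

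| Outcome | Planned summary | Difference from oxybutynin with CI |
|---|---|---|
| Maximum cystometric capacity | ANCOVA | Yes (SAP 8.2.1) |
| Tier 1 adverse events | Percentages, risk differences, p-values | Yes (SAP 8.2.5) |
| Tier 2 adverse events | Percentages, risk differences | Yes (SAP 8.2.5) |
| Acuity, accommodation, CBCL, Grooved Pegboard | Values and changes by visit | No |
| Pulse | Change, and counts below 40 or above 120 | No |

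**2. The plan's own precision figures.** Protocol 9.1 assumes 33 evaluable subjects per arm and an SD of 120 mL.
- Within-arm power for a 70 mL change, by noncentral t with noncentrality (70/120) × √33 = 3.35, is 90.1%. The stated figure of at least 90% reproduces.
- The half-width for a difference is t(0.975, 64) × SD × √(2/33) = 1.998 × 120 × 0.246 = 59.0 mL expected. It is 65.5 mL when the SD is taken at its 90th percentile. The stated figure of about ±70 mL is slightly conservative.
- In SD units, 70/120 = 0.58. The plan therefore already accepts ±0.58 SD as informative for comparing efficacy with oxybutynin.

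**3. The same interval for the safety tests.** The documents give no SDs for these, so results are in SD units and take 33 per arm as available.
- Unadjusted: 1.998 × √(2/33) = 0.49 SD of the score analysed (0.55 SD with 90% assurance).
- Baseline-adjusted, in SDs of the Week 12 score: multiply by √(1 − r²). At assumed r = 0.5, 0.7 and 0.8 this gives 0.43, 0.35 and 0.30.
- Baseline-adjusted, in SDs of the change score: multiply by √((1 + r)/2). The same correlations give 0.43, 0.45 and 0.47. The two sets describe the same intervals in different units.
- Pulse, if the SD of change is assumed to be 8 to 15 bpm: 0.492 × 8 = 3.9 bpm to 0.492 × 15 = 7.4 bpm, unadjusted.

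**4. Grooved Pegboard by version.** The SAP reports the 10-peg and 25-peg tests separately. If 33 per arm split 22 and 11 (assumed), the unadjusted half-widths are 2.018 × √(2/22) = 0.61 SD and 2.086 × √(2/11) = 0.89 SD.

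**5. Effect of the split columns.** If one oxybutynin column held 16 or 11 subjects (assumed) against 33 on fesoterodine, the half-width would be 0.61 or 0.70 SD, from t × √(1/33 + 1/16) or t × √(1/33 + 1/11). That contrast would also no longer be randomised.

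**6. Illustration of within-arm change.** Assume a gain shared by all arms and a drug harm of 0.3 SD in one arm. With a shared gain of 0.1, 0.3 or 0.5 SD, the harmed arm changes by −0.2, 0 or +0.2 SD. The randomised difference is 0.3 SD in every case.

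**The case against.** Descriptive reporting is consistent across protocol and SAP, and the SAP describes safety analysis as generally exploratory. An objective to evaluate safety does not oblige the sponsor to give an interval for every measure. This stands as a reason not to call the plan defective. It is not a reason to omit an interval labelled as estimation: the SAP went beyond the protocol's descriptive comparison of adverse event rates by adding risk differences with CIs.

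Little information is lost. The tables give n, mean and SD of change, so a reader could pool the three oxybutynin groups exactly and form an unadjusted difference and interval. In the illustration above, the contrast between arms would be visible in the same table. This also stands. What a reader cannot recover is the baseline-adjusted difference, and the pooling is left to the reader.

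The intervals are wide. An observed difference of 0.3 SD lies inside half-widths of 0.49, 0.43 and 0.35 and only just exceeds the best case (0.295 before rounding). That stands and limits what the addition can deliver.

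One might argue that the rule analysing all secondary endpoints like the primary already supplies the contrast, since Protocol 2.2.2 lists safety endpoints as secondary. That rule sits under Efficacy Analysis in the protocol, SAP 6.1.2 lists only efficacy endpoints as secondary, and the specific safety rules are descriptive. It does not fill the gap.

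**Conclusion.** The omission is real but limited. For Grooved Pegboard, CBCL, visual acuity, accommodation and pulse, Cohort 1 has no planned fesoterodine-oxybutynin difference or interval, and the specified columns do not show the oxybutynin arm intact at Week 12. Adding the contrast is a worthwhile, inexpensive improvement.

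Three stronger conclusions that a reader might infer are not supported:

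- **That the whole safety comparison with oxybutynin rests on within-arm change.** Tier 1 and Tier 2 adverse events have planned contrasts, and monitored events include anticholinergic, CNS and visual effects. Which of these are Tier 1 depends on the Safety Review Plan, which is not among the documents.
- **That the measured tests are, as a group, better protected from open-label influence than adverse event reports.** Protocol 7.2.8 has the CBCL completed by a parent or caregiver, who knows the treatment. Acuity and accommodation depend on the child's response. The argument fits Grooved Pegboard time and pulse best, and only in degree.
- **That practice effects distort all these measures.** The argument is plausible mainly for the Grooved Pegboard, and the documents give no estimate for any measure.

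The precision figures assume 33 subjects per arm with data on each test, and the correlations are assumed. On that basis the intervals could bound moderate differences but would not reliably resolve one of about 0.3 SD.

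**What to change.** In SAP 8.2.5, add for Cohort 1 a baseline-adjusted mean difference (each fesoterodine dose minus oxybutynin) with a 95% CI and no test, labelled exploratory estimation. Use the Active Comparator Phase safety set that SAP 5.3 already defines, with three groups: fesoterodine 4 mg, fesoterodine 8 mg and one intact oxybutynin arm. Specify in advance:

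- **Grooved Pegboard, Week 12:** completion time for the dominant hand, with peg version (10 or 25) as a stratum or analysed separately.
- **CBCL, Week 12:** Total Score.
- **LogMAR acuity and accommodation, Week 12:** one pre-specified summary per subject across the two eyes.
- **Pulse:** Weeks 4 and 12.

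Keep the descriptive tables. No new data or subjects are needed.

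The cost is SAP wording and a small set of tables. With Grooved Pegboard version as a stratum there are (4 Week 12 measures + 2 pulse time points) × 2 comparisons = 12 intervals; analysing the two versions separately gives 14. Without multiplicity control, about 12 × 0.05 = 0.6 of the 12 would be expected to exclude zero if there were no true differences, so the tables should say they are for estimation only.

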**8.2.6. Summary of Efficacy Endpoint Analyses**

| Endpoint  | Analysis Set    | Assessment | PLANNED Statistical Method   | Missing Data                | Interpretation                                    |
|---|-----------------|------------|--|-----------------------------|---|
| Change in maximum cystometric bladder capacity at week 12 relative to baseline                  | FAS (Cohort 1)  | Week 12    | ANCOVA – hypothesis testing approach; Descriptive statistics and subgroup summaries. | BOCF/LOCF (for ANCOVA only) | Primary analysis (for Cohort 1)                   |
|   | FAS (Cohort 2)  | Week 12    | ANCOVA – estimation approach; Descriptive statistics and subgroup summaries.         | BOCF/LOCF (for ANCOVA only) | Primary analysis (for Cohort 2)                   |
|   | PPAS (Cohort 1) | Week 12    | ANCOVA – hypothesis testing approach; Descriptive statistics.                        | No imputation               | Supportive to the primary analysis (for Cohort 1) |
|   | PPAS (Cohort 2) | Week 12    | ANCOVA – estimation approach; Descriptive statistics.                                | No imputation               | Supportive to the primary analysis (for Cohort 2) |
| Change in maximum detrusor pressure at maximum bladder capacity at week 12 relative to baseline | FAS (Cohort 1)  | Week 12    | ANCOVA – hypothesis testing approach; Descriptive statistics.                        | BOCF/LOCF (for ANCOVA only) | Secondary analysis (for Cohort 1)                 |
|   | FAS (Cohort 2)  | Week 12    | ANCOVA – estimation approach; Descriptive statistics.                                | BOCF/LOCF (for ANCOVA only) | Secondary analysis (for Cohort 2)                 |
| Presence of IDC   | FAS (Cohort 1)  | Week 12    | Categorical summaries  | BOCF/LOCF                   | Secondary analysis (for Cohort 1)                 |
|   | FAS (Cohort 2)  | Week 12    | Categorical summaries  | BOCF/LOCF                   | Secondary analysis (for Cohort 2)                 |
|   | PPAS (Cohort 1) | Week 12    | Categorical summaries  | No imputation               | Secondary analysis (for Cohort 1)                 |

| Endpoint  | Analysis Set    | Assessment | PLANNED Statistical Method                                    | Missing Data                | Interpretation                    |
|---|-----------------|------------|---|-----------------------------|-----------------------------------|
|   | PPAS (Cohort 2) | Week 12    | Categorical summaries   | No imputation               | Secondary analysis (for Cohort 2) |
| Change in bladder compliance at week 12 relative to baseline                        | FAS (Cohort 1)  | Week 12    | ANCOVA – hypothesis testing approach; Descriptive statistics. | BOCF/LOCF (for ANCOVA only) | Secondary analysis (for Cohort 1) |
|   | FAS (Cohort 2)  | Week 12    | ANCOVA – estimation approach; Descriptive statistics.         | BOCF/LOCF (for ANCOVA only) | Secondary analysis (for Cohort 2) |
|   | PPAS (Cohort 1) | Week 12    | ANCOVA – hypothesis testing approach; Descriptive statistics. | No imputation               | Secondary analysis (for Cohort 1) |
|   | PPAS (Cohort 2) | Week 12    | ANCOVA – estimation approach; Descriptive statistics.         | No imputation               | Secondary analysis (for Cohort 2) |
| Change in Bladder volume at first IDC at week 12 relative to baseline               | FAS (Cohort 1)  | Week 12    | ANCOVA – hypothesis testing approach; Descriptive statistics. | BOCF/LOCF (for ANCOVA only) | Secondary analysis (for Cohort 1) |
|   | FAS (Cohort 2)  | Week 12    | ANCOVA – estimation approach; Descriptive statistics.         | BOCF/LOCF (for ANCOVA only) | Secondary analysis (for Cohort 2) |
| Change in mean number of micturitions per 24 hours at Week 12 relative to baseline. | FAS (Cohort 1)  | Week 12    | ANCOVA – hypothesis testing approach; Descriptive statistics. | BOCF/LOCF (for ANCOVA only) | Secondary analysis (for Cohort 1) |
|   | FAS (Cohort 2)  | Week 12    | ANCOVA – estimation approach; Descriptive statistics.         | BOCF/LOCF (for ANCOVA only) | Secondary analysis (for Cohort 2) |
| Change in mean number of incontinence episodes per 24                               | FAS (Cohort 1)  | Week 12    | ANCOVA – hypothesis testing approach; Descriptive statistics. | BOCF/LOCF (for ANCOVA only) | Secondary analysis (for Cohort 1) |

| Endpoint   | Analysis Set   | Assessment | PLANNED Statistical Method                                    | Missing Data                | Interpretation                    |
|--|----------------|------------|---|-----------------------------|-----------------------------------|
| hours at Week 12 relative to the baseline  | FAS (Cohort 2) | Week 12    | ANCOVA – estimation approach; Descriptive statistics.         | BOCF/LOCF (for ANCOVA only) | Secondary analysis (for Cohort 2) |
| Change in mean number of urgency episodes per 24 hours at Week 12 relative to the baseline | FAS (Cohort 1) | Week 12    | ANCOVA – hypothesis testing approach; Descriptive statistics. | BOCF/LOCF (for ANCOVA only) | Secondary analysis (for Cohort 1) |
|  | FAS (Cohort 2) | Week 12    | ANCOVA – estimation approach; Descriptive statistics.         | BOCF/LOCF (for ANCOVA only) | Secondary analysis (for Cohort 2) |
| Change in mean voided volume per micturition at Week 12 relative to baseline.              | FAS (Cohort 1) | Week 12    | ANCOVA – hypothesis testing approach; Descriptive statistics. | BOCF/LOCF (for ANCOVA only) | Secondary analysis (for Cohort 1) |
|  | FAS (Cohort 2) | Week 12    | ANCOVA – estimation approach; Descriptive statistics.         | BOCF/LOCF (for ANCOVA only) | Secondary analysis (for Cohort 2) |

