### **2.2.2. Secondary Endpoints**

#### **2.2.2.1. Efficacy Endpoints**

- Detrusor pressure at maximum bladder capacity.
- Presence of involuntary detrusor contractions (IDC).
- Bladder volume at first IDC.
- Bladder compliance.
- Mean number of micturitions and/or catheterizations/24 hrs.
- Mean number of incontinence episodes/24 hrs.
- Mean urgency episodes/24 hrs if applicable (only for sensate subjects).
- Mean volume voided per micturition or mean volume per catheterization.

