### **9.2.2. Analysis of Primary Endpoint**

#### **9.2.2.1. Cohort 1 (>25 kg)**

Change from baseline to Week 12 in the primary endpoint will be analysed using an ANCOVA including terms for treatment group, baseline (for the endpoint being analyzed) and weight. The Least Squares mean change from baseline for each treatment group, standard error, 95% confidence intervals and p-values associated with the Least Squares mean changes from baseline will be presented.

All endpoints will also be summarized descriptively for each treatment group, by timepoint, using: N, mean, standard deviation, median, minimum and maximum. Should any of the assumptions of the analysis methods not be adequately met, alternative procedures will be used and fully documented.

The following primary comparisons of interest will be assessed:

- Change from Baseline to Week 12 for fesoterodine 4 mg.
- Change from Baseline to Week 12 for fesoterodine 8 mg.

The Least Squares means and 95% confidence intervals for the difference between each fesoterodine dose group and oxybutynin will also be calculated.

The following secondary comparisons will be assessed using 95% confidence intervals for the difference between treatment means (for the change from baseline to Week 12):

- Fesoterodine 4 mg vs Oxybutynin.
- Fesoterodine 8 mg vs Oxybutynin.

As these secondary comparisons are based on an estimation approach, no formal statistical hypothesis testing will be performed. Conclusions will be based on point estimates and confidence intervals.

The primary analysis will be based on the Cohort 1 Full Analysis Set (FAS1). The secondary analysis set will be the Cohort 1 Per Protocol Analysis Set (PPAS1).

For the PPAS analysis no imputation techniques for missing data will be employed. For the FAS analysis a Baseline Observation Carried Forward (BOCF) and a Last Observation Carried Forward (LOCF) algorithm will be used for missing data.

Data from the active comparator phase for this cohort may be summarised, analysed and reported after all subjects in this cohort have either completed or withdrawn prior to the Week 12 visit (ie, prior to formal completion of the study). The results of these analyses will be available to limited members of the study team as a management tool in order to aid decision making, and may also be shared with regulators in order to facilitate timely discussion of the overall program; they will not be used to stop or modify the design of the study.

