#### **9.2.2.2. Cohort 2 ( $\leq 25$ kg)**

Change from baseline to Week 12 in the primary endpoint will be analyzed using an ANCOVA including terms for treatment group and baseline (for the endpoint being analyzed). The Least Squares mean change from baseline for each treatment group, standard error and 95% confidence intervals associated with the Least Squares mean changes from baseline will be presented.

All endpoints will also be summarized descriptively for each treatment group, by timepoint, using: N, mean, standard deviation, median, minimum and maximum. Should any of the assumptions of the analysis methods not be adequately met, alternative procedures will be used and fully documented.

The following primary comparisons of interest will be assessed:

- Change from Baseline to Week 12 for fesoterodine 2 mg.
- Change from Baseline to Week 12 for fesoterodine 4 mg.

As these comparisons are based on an estimation approach, no formal statistical hypothesis testing will be performed. Conclusions will be based on point estimates and confidence intervals.

The primary analysis will be based on the Cohort 2 Full Analysis Set (FAS2). The secondary analysis set will be the Cohort 2 Per Protocol Analysis Set (PPAS2).

For the PPAS analysis no imputation techniques for missing data will be employed. For the FAS analysis a Baseline Observation Carried Forward (BOCF) and a Last Observation Carried Forward (LOCF) algorithm will be used for missing data.

Data from the efficacy phase for this cohort may be summarized, analyzed and reported after all patients in this cohort have either completed or withdrawn prior to the Week 12 visit (ie, prior to formal completion of the study). The results of these analyses will be available to limited members of the study team as a management tool in order to aid decision making, and may also be shared with regulators in order to facilitate timely discussion of the overall program; they will not be used to stop or modify the design of the study.

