### **9.2.3. Analysis of Secondary Endpoints**

All secondary endpoints will be analysed using the same methods as the primary endpoint for each cohort.

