### **8.1.2. Analysis of Binary Data**

Binary endpoints will be presented using cell counts and proportions for each response category. For summaries of change from baseline the tables will be presented as a cross tabulation with baseline visit along the side and week 12 results along the top.

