### **8.2.3. Secondary Analyses**

All secondary endpoints will be analysed as for the primary analyses as defined for each respective cohort using the appropriate full analysis set. A further analysis of the key secondary endpoints of Bladder compliance and IDC will use the per protocol analysis set.

The presence of IDC will be analyzed as for discrete endpoints.

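### Presence of IDC, named a key secondary endpoint in SAP 8.2.3, is planned with no confidence interval in either cohort and no contrast with oxybutynin in Cohort 1

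*SAP*

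**What the plan says.** Protocol 2.2.2.1 lists presence of IDC among the secondary efficacy endpoints. Protocol 9.2.3 sets one rule for all of them: "All secondary endpoints will be analysed using the same methods as the primary endpoint for each cohort".

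For Cohort 1 those methods (Protocol 9.2.2.1) include, within each arm, "The Least Squares mean change from baseline for each treatment group, standard error, 95% confidence intervals and p-values associated with the Least Squares mean changes". They also include the comparison with the active control: "The Least Squares means and 95% confidence intervals for the difference between each fesoterodine dose group and oxybutynin will also be calculated". For Cohort 2 (Protocol 9.2.2.2) there is no testing and no oxybutynin arm, but intervals are still required: "Conclusions will be based on point estimates and confidence intervals".

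SAP 8.2.3 repeats the general rule, singles out bladder compliance and IDC as key secondary endpoints for a further per-protocol analysis, and then makes an exception: "The presence of IDC will be analyzed as for discrete endpoints". SAP 8.1.2 says what that means: "Binary endpoints will be presented using cell counts and proportions for each response category", with change from baseline shown as a cross-tabulation of baseline against Week 12. The table in SAP 8.2.6 gives "Categorical summaries" in all four IDC rows (FAS and PPAS, Cohorts 1 and 2).

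**The concern.** Presence of IDC is the only endpoint in the SAP 8.2.6 table without a method that yields an interval. Every other row, including bladder compliance, the other key secondary endpoint, is an ANCOVA. Comparing the efficacy of fesoterodine with oxybutynin in the heavier cohort is a stated secondary objective (Protocol 2.1.2), and on this endpoint the plan leaves that comparison to the eye.

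With about 33 evaluable subjects per arm, percentages move a good deal by chance. A table without intervals does not show how far apart two arms could truly be. If intervals are added later, their method will be chosen after the data are seen, and with counts this small the method can matter.

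**Working it through.** **Which IDC endpoint is meant.** SAP 8.2.3 says only IDC. The SAP 8.2.6 table gives PPAS rows to presence of IDC and none to bladder volume at first IDC, so presence is the key secondary endpoint.

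**The primary method against what IDC receives.**

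| Element | Primary, Cohort 1 | Primary, Cohort 2 | Presence of IDC |
|---|---|---|---|
| Within-arm change with 95% CI | yes | yes | no |
| Within-arm p-value | yes | no | no |
| 95% CI v oxybutynin | yes | not applicable | no |
| Counts, proportions, cross-tabulation | not applicable | not applicable | yes |

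So the missing interval concerns both cohorts, and the missing contrast and p-value concern Cohort 1 only.

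**What the SAP does for other binary outcomes.** In SAP 8.2.5, Tier 1 and Tier 2 adverse events in Cohort 1 get a risk difference against oxybutynin with a 95% CI. An event reaching Tier 2 because 4 subjects in one arm had it therefore gets a between-arm interval. A key efficacy endpoint of the same type does not.

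**The plan's own figures.** Protocol 9.1 gives 33 per arm, a 70 mL change, SD 120 mL and two-sided 5%. The noncentrality is (70/120) × √33 = 3.35, and the one-sample t-test power is 0.901, so the stated figure of at least 90% reproduces. For Cohort 2 (25 per arm), the interval half-width at 80% probability is 55.0 mL, as stated. These figures concern bladder capacity. No precision is stated for IDC.

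**Precision of an IDC contrast in Cohort 1.** The documents give no IDC rates, so equal observed proportions of about 0.2 to 0.8 are assumed, with 33 per arm. The Newcombe interval is built from the Wilson limits (l, u) of each arm. With equal proportions p, its half-width is √[(p − l)² + (u − p)²].

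| Each arm | p | Wilson 95% limits | Half-width of difference |
|---|---|---|---|
| 7/33 | 0.212 | 0.107 to 0.378 | √(0.105² + 0.166²) = 0.196 |
| 12/33 | 0.364 | 0.222 to 0.534 | 0.222 |
| 16/33 | 0.485 | 0.325 to 0.648 | √(0.160² + 0.163²) = 0.228 |
| 21/33 | 0.636 | 0.466 to 0.778 | 0.222 |
| 26/33 | 0.788 | 0.622 to 0.893 | 0.196 |

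Identical percentages would thus be compatible with a true difference of about 20 to 23 points either way. An illustrative unequal pair, 20/33 v 26/33, gives −18 points with a 95% CI of −38 to +4.

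**Precision within one arm.** Over the same range, the Wilson half-width for a single proportion is about 13 to 16 points at 33 per arm and 15 to 18 points at 25 per arm.

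**Paired change within one arm (illustrative counts, n = 33).** Let b subjects lose IDC and c gain it. The change is (b − c)/n, with Wald standard error √[(b + c) − (b − c)²/n]/n. The exact McNemar p is twice the lower binomial tail of min(b, c) in b + c trials at 0.5.

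- b = 12, c = 4: net fall 8/33 = 24 points. SE = √(16 − 64/33)/33 = 0.114. 95% CI 2 to 47 points. Exact p = 0.077.
- b = 8, c = 2: net fall 6/33 = 18 points. 95% CI 0.5 to 36 points. Exact p = 2 × 56/1024 = 0.109.

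In both cases the Wald interval excludes zero while the exact test does not reach 5%. That is why the method should be named in advance.

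**The case against.** A reader might infer that the SAP breaches the protocol. It does not. The opening of Protocol section 9 lets the SAP modify the planned analyses and asks for an amendment only for major changes to the primary endpoint or its analysis. The SAP is also coherent here: SAP 8.2.3 gives a general rule and then a specific exception, and SAP 8.1.2 and 8.2.6 carry it through. Moving a yes/no outcome away from ANCOVA is right. What remains is that nothing equivalent was put in its place and no reason is given.

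A reader might also infer that bare counts are all that is planned. In fact proportions and a cross-tabulation are planned, and the cross-tabulation holds the discordant cells. Someone could compute intervals from it, which lowers the stakes. It does not settle which interval would be used, or whether it would account for baseline.

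Nor should IDC be presented as the single direct measure of the disease. Inclusion criterion 2 admits subjects on detrusor overactivity or on decreased compliance, so some may have no IDC at baseline. Bladder volume at first IDC is a companion measure and does get ANCOVA. The key label appears only in SAP 8.2.3; the protocol has no such tier.

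Two technical objections stand and shape the fix. An unadjusted Week 12 risk difference ignores baseline IDC, whereas the primary ANCOVA adjusts for baseline. On the FAS, a subject whose baseline value is carried forward counts as unchanged by construction, which pulls the paired change towards zero.

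**Conclusion.** The point holds as a gap in method. Presence of IDC has no interval in either cohort and no oxybutynin contrast in Cohort 1, while the SAP plans exactly that kind of contrast for adverse events. It is not a protocol breach or a numerical error, and the p-value and contrast are not missing from Cohort 2, which was never meant to have them.

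The size rests on assumed inputs: 33 evaluable per arm, equal observed proportions of about 0.2 to 0.8, and an unadjusted interval. The range of plus or minus 20 to 23 points is a statement about precision, not a forecast of results. The unequal and paired counts are illustrations only.

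Severity is low. No sample size or primary conclusion depends on IDC.

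**What to change.** In SAP 8.1.2, 8.2.3 and 8.2.6, add:

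- For each arm in both cohorts, the paired change in the proportion with IDC from baseline to Week 12, with a 95% CI whose method is named. An exact McNemar p-value in Cohort 1 is optional.
- For Cohort 1, the Week 12 difference of each fesoterodine dose minus oxybutynin with a 95% CI, preferably adjusted for baseline IDC, for example a standardised risk difference from a logistic model. State in advance that the unadjusted Newcombe interval is used if the model does not fit.
- A note that subjects with the baseline value carried forward count as no change on the FAS. Keep FAS and PPAS as planned.

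The cost is a few lines of SAP text and standard code on tables already planned; no new data or visits are needed. The downside is a few more secondary intervals without multiplicity adjustment, which should be labelled as such.
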